Aim 1: To determine the impact of vaginally delivered estrogen on global impression of improvement in women with symptomatic stage I-III pelvic organ prolapse who are undergoing pelvic floor physical therapy. Women will be randomized to PFPT in combination with vaginal estrogen versus placebo, and will be administered questionnaires at baseline and 6 months after treatment. The primary outcome is global impression of her improvement, measured via administration of the validated Patient Global Impression of Improvement questionnaire (PGI-I).¹⁰ Other validated questionnaires will be used to assess symptoms, sexual function, and guality of life. Results will be compared between groups.

Aim 2: To determine the impact of vaginal estrogen on POP stage, as measured by the Pelvic Organ Prolapse Quantification (POP-Q) exam. The POP-Q exam is an objective validated clinical tool that is used to assess prolapse stage.¹¹ POP-Q exam will be performed at baseline and 6 months after treatment.

Aim 3: To evaluate the effect of PFPT and vaginal estrogen on biomarkers of prolapse, and to correlate this data with patient symptoms and anatomical changes. Vaginal tissue swabs will be collected at baseline and 6 months. Collagenase activity will be analyzed.

BACKGROUND

Estrogen receptors are present throughout the female pelvic floor and have been detected in the levator ani muscles and urogenital ligaments. This biological finding provides a basis for the suggestion that estrogen may play a role in the development of pelvic organ prolapse, and in turn, may be beneficial in the prevention and treatment of this condition. Several studies have confirmed that the degradation of pelvic connective tissues is regulated by hormones. In primates, estradiol given to ovariectomized animals increased collagen synthesis and the expression of vaginal cystatin C, an inhibitor of collagen proteases. In human studies, biopsy specimens of the arcus tendineous fasciae pelvis in postmenopausal women who were not on hormones showed a decrease in type I collagen and collagen ratios compared to biopsies from premenopausal women, whereas no decrease was found in postmenopausal women who were on hormone therapy. 16

Additional studies on human tissue and in rats also suggest that hormones may have a protective effect against supportive tissue degradation^{8,9} and may lead to restoration of biomechanical properties.¹⁷

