- I. Demographic data will be abstracted from the medical record by the research staff. Research variables include: age, race, ethnicity, BMI, age at menarche, history of oral contraceptive use, gravidity, parity, vaginal parity, number of cesarean sections, age at first full term pregnancy, age at last full term pregnancy, weight of largest baby, date of last/final menstrual period, age at menopause, time since menopause, current medications, smoking status, bowel habits, questions related to urinary and fecal incontinence, medical comorbidities (obesity, diabetes, chronic lung disease, constipation and irritable bowel syndrome), and surgical history (focusing on abdominopelvic surgeries and hernia repairs).
- II. All subjects will complete self-administered questionnaires. Pelvic floor symptoms will be assessed with the Pelvic Floor Distress Inventory (PFDI-20).²³ Sexual activity will be evaluated with the Pelvic Organ Prolapse Urinary Incontinence Sexual Questionnaire (PISQ-12).²⁴ Impact on quality of life will be measured with the Pelvic Floor Impact Questionnaire (PFIQ-7).²³ All of these questionnaires have been validated in women with pelvic organ prolapse.
- III. POP-Q exam, as described by the International Continence Society, is performed on all patients at their initial visit to the Women's Center for Bladder and Pelvic Health. As stated in the inclusion criteria above, only those patients who have stage I, II, or III prolapse on POP-Q exam will be approached for study participation.
- IV. A vaginal maturation index will be obtained on all patients in order to assess baseline estrogen status.

- V. Vaginal swabs will be collected from the posterior fornix for biochemical analysis. The vaginal swabs will be sent to [name] laboratory where collagenase activity will be measured.
- VI. Subjects will be randomized to receive either PFPT plus vaginal estrogen or placebo. A random allocation sequence will be achieved by generating a random number list using a computer.

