- VII. Subjects will be given a 6 month supply of either vaginal estrogen or placebo and instructed on proper use (1 gram every night for 7 days, then 1 gram twice weekly thereafter for a total duration of 6 months). Handouts will be given which include these instructions and the potential side effects of vaginal estrogen therapy. The dose of hormones used in this study is the same as what we commonly prescribe in our office during routine clinical care. Several trials have evaluated the safety of vaginally delivered estrogen and reports of endometrial hyperplasia or cancer are rare. ²⁵⁻³⁰

VIII. All patients will be referred to the UPMC Centers for Rehab Services for PFPT for a treatment duration of 6 months. All women will undergo the standard PFPT program used in the treatment of prolapse. This includes weekly sessions for the first 4 weeks, followed by 1 session per month thereafter, with instructions for home practice.

Interventions – Follow-up:

- I. Phone call at 3 months: Subjects will receive a phone call from the research staff at 3 months following the initial baseline visit to assess compliance with therapy and to address questions.
- II. Follow-up visit at 6 months: Patients will be seen at the Women's Center for Bladder and Pelvic Health 6 months after initiation of therapy. The following activities will take place:
 - a. Questionnaire completion: Subjects will complete the same 3 questionnaires that they completed at their baseline visit (PFDI-20,²³ PISQ-12,²⁴ and PFIQ-7 ²³). The Patient Global Impression of Improvement questionnaire (PGI-I) will also be completed, which is a global assessment tool that has been validated in women undergoing treatment for prolapse.¹⁰
 - b. Patients will be asked to complete a brief confidential survey about the number of PFPT visits that they attended and the reason for any PFPT visits that were missed. This survey will also ask about vaginal symptoms over the course of the study, and about compliance with study drug therapy. In order to maintain blinding of the research staff, patients will fill out this survey in private and will place it in a sealed envelope when finished.
 - c. POP-Q examination will be performed
 - d. Vaginal maturation index and vaginal swabs for biochemical analysis will be collected

Primary outcome: Global impression of improvement with treatment, as measured by the PGI-I¹⁰

Secondary outcomes:

- Pelvic floor symptoms as measured by the PFDI-20 ²³

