- Sexual complaints as measured by the PISQ-12 ²⁴
- Impact on quality of life as measured by the PFIQ-7²³
- POP-Q stage
- Biochemical markers collagenase activity

Data analysis:

Baseline characteristics will be analyzed using chi-square, Student's t-, or Mann-Whitney U test, as appropriate. Paired Student's t-test or Wilcoxon signed-rank test will be used to compare baseline and 6-month questionnaire scores, biochemical endpoints, and POP-Q measurements, as appropriate based on the distributions of the data. Student's t- or Mann-Whitney U test will be used to compare the change between the baseline and 6-month measurements between groups. Pearson's correlation coefficient and multivariable linear regression models will be used to examine the associations between clinical and biochemical outcomes. Statistical tests will be evaluated at the 0.05 significance level.

Safety Monitoring:

The risks associated with the use of vaginal estrogen are small, ²⁵⁻³⁰ and in this study, patients will be on hormones for only 6 months. Patients will be instructed to contact the research team in the event of any symptoms, such as breast tenderness, perineal pain, vaginal discharge, or bleeding. Persistent breast or perineal pain may require a decrease in the frequency of vaginal estrogen use. All bleeding will be evaluated by standard clinical guidelines. Several trials have evaluated the safety of vaginally delivered estrogen and reports of endometrial hyperplasia or cancer are rare. ²⁵⁻³⁰ At the discretion of the investigators, if continued study participation is felt to be unsafe for any woman, she will be withdrawn from the study. Drs. [name] and [name] will be responsible for monitoring for adverse events and side effects. Formal monitoring will take place at monthly research meetings which the investigators attend. Informal monitoring will occur more frequently and will be based upon need. All deviations from the normal course will be reported to the IRB.

Subject compensation:

Subjects will be provided with enough vaginal medication for the 6-month study duration. Study subjects will be compensated \$50 at their baseline visit and \$50 at their 6-month follow-up visit, for a total of \$100. Patients will also be reimbursed \$25 for each PFPT session attended, up to 9 sessions (for a total of \$225). A grant has been received from the American Urogynecologic Society which will cover the cost of this compensation.

Timetable:

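### Does the plan leave the primary outcome, PGI-I, without a usable between-group test because its only such test is on change from baseline?

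*Combined protocol and SAP*

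**What the plan says.** The Primary outcome entry names the PGI-I alone. The Secondary outcomes list has five entries: PFDI-20, PISQ-12, PFIQ-7, POP-Q stage and collagenase activity.

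Aim 1 says that women "will be administered questionnaires at baseline and 6 months after treatment", names the PGI-I as primary, adds "Other validated questionnaires will be used to assess symptoms" among other things, and closes with "Results will be compared between groups".

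The visit schedule is itemised. Item II of the Baseline Visit lists three questionnaires (PFDI-20, PISQ-12, PFIQ-7) and does not mention the PGI-I. Item II.a of the Follow-up says of the 6-month visit: "Subjects will complete the same 3 questionnaires that they completed at their baseline visit". It then adds the PGI-I as a further instrument at that visit.

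Two sentences in Data analysis concern the comparison of outcomes. One is within-patient: "Paired Student's t-test or Wilcoxon signed-rank test will be used to compare baseline and 6-month questionnaire scores", extended to the biochemical and POP-Q measurements. The other is between-group: "Student's t- or Mann-Whitney U test will be used to compare the change between the baseline and 6-month measurements between groups".

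**The concern.** Both outcome-comparison sentences presuppose a baseline value, and the primary outcome has none. The remaining sentences do not fill the gap. The one naming chi-square, t and Mann-Whitney tests is confined to baseline characteristics, and the one on correlation and regression concerns links between clinical and biochemical outcomes, not treatment arms. On a literal reading, no sentence says how the sole primary outcome is compared between estrogen and placebo.

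Aim 1 seems to make this worse. It speaks of questionnaires at two visits just before naming the PGI-I, so a reader may wonder whether a baseline PGI-I was intended.

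The stake would be an analyst left free to choose the primary analysis after seeing the data, or one who tries to build a change score that does not exist.

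**Working it through.** The question is one of text, so the outcomes are set against the visits and the rule.

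| Outcome | Baseline | 6 months | Change score exists |
|---|---|---|---|
| PFDI-20 | yes (Baseline Visit, II) | yes (Follow-up, II.a) | yes |
| PISQ-12 | yes (II) | yes (II.a) | yes |
| PFIQ-7 | yes (II) | yes (II.a) | yes |
| POP-Q stage | yes (III) | yes (II.c) | yes |
| Collagenase activity | yes (V) | yes (II.d) | yes |
| PGI-I (primary) | no | yes (II.a) | no |

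The change rule therefore fits 5 of 5 secondary outcomes and 0 of 1 primary. The literal point is correct. Three further steps decide whether it matters.

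**1. When is the PGI-I given?** Aim 1's statement about two visits is true of the questionnaires as a set. It does not say that every instrument is given twice. The itemised schedule is specific: three instruments at baseline, the same three at 6 months, and the PGI-I in addition at 6 months. The detailed text settles the summary, and there is no contradiction to resolve. A baseline PGI-I would also make no sense, because a woman cannot rate improvement under a treatment she has not started.

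**2. What would the analyst do?** The PGI-I score at 6 months is already a judgement of change since baseline, so it plays the part that the change score plays for the other five outcomes. Aim 1 asks for a comparison between groups, and Data analysis names the two-sample tests. Together these give a t or Mann-Whitney comparison of the 6-month PGI-I between arms.

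Simple algebra confirms that nothing is lost. Let *Y* be the 6-month score and let every woman have the same notional starting value *c* (no change yet). The change score is *D* = *Y* − *c*. Then

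- mean(*D*, estrogen) − mean(*D*, placebo) = mean(*Y*, estrogen) − mean(*Y*, placebo), and the variances are unchanged, so the t statistic is the same;
- subtracting a constant leaves every rank unchanged, so the Mann-Whitney statistic is the same.

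The rule as worded and the natural reading thus give the same p-value.

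**3. Does the open choice between two tests matter?** The documents give no PGI-I distribution and no number of response categories, so any figure is illustrative. The check assumed seven distributions (six on seven categories, one on five), 27 against 26 women, two-sided 0.05 and 100,000 null trials per setting. The Monte Carlo standard error is √(0.05 × 0.95 / 100,000) ≈ 0.0007.

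| Quantity under the null | Lowest | Highest |
|---|---|---|
| Type I error, t-test | 4.81% | 5.05% |
| Type I error, Mann-Whitney | 4.75% | 4.87% |
| Two tests disagree at 0.05 | 0.68% | 2.45% |
| Type I error, smaller p-value of the two | 5.22% | 6.05% |

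Either test used alone keeps its size. The last row describes a practice that the plan does not propose. Even there the largest excess over the nominal level is 6.05 − 5.00 = 1.05 percentage points.

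The Sample size section is not touched. The 53 women (27 + 26) were set by budget, and the power statement rests on primate collagen and collagenase data, not on the PGI-I.

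**The case for a change.** The strongest reply is that a plan should state its primary analysis, not leave it to be inferred. This is the only primary outcome, one extra sentence would cost almost nothing, and the between-group sentence gives no rule for choosing between its two tests. The phrase about choosing by the distribution of the data sits in the within-patient sentence, not in the between-group one.

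The description is accurate: the test for the PGI-I must be inferred, and the choice between two tests is open. It does not amount to a defect that alters a result. Only one sensible inference is available. The choice of test is equally open for all five secondary outcomes, so it does not arise from the missing PGI-I baseline. Nothing in the documents or in the check above shows that either test is wrong, so fixing one is a matter of preference.

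Timing also limits what a clarification could add. The Timetable hoped to complete data collection by August 2014, and the cover is dated September 2016. Whether outcomes had been seen by then is not stated. If they had, a sentence added at that date would be post hoc and could not count as prespecification.

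**Conclusion.** No change to the plan is needed. The wording slip is real: the only between-group rule for outcomes is phrased for change from baseline, and the primary outcome has a single 6-month value. Its effect on the analysis is nil under the natural reading, because the 6-month PGI-I is already a rating of change and either named test can be applied to it directly. The undecided choice between the two tests is worth about one percentage point of type I error at most, and only if both were run and the better one kept.

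This rests on two things. The itemised visit schedule is taken to govern over Aim 1's summary sentence. The error-rate figures rest on assumed PGI-I distributions, because the documents give none; the reading of the text does not depend on them. In a pilot with a convenience sample, meant to inform a larger trial, this is a gap that a competent analyst fills correctly without instruction.

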Sample size: Given the lack of data on PFPT and vaginal estrogen in the treatment of prolapse, the decision was made to conduct a pilot study, with plans to use this data as a foundation for instituting a larger clinical trial in the future. A convenience sample size of 53 patients (27 in the treatment group and 26 controls) was chosen to comply with the budget. Based on prior data from our lab evaluating collagen alignment and

collagenase activity in primates with mild versus no prolapse,^{21,22} we estimate that 53 patients will have 99.6% power to detect a 48% difference between groups at the 2-sided 0.05 significance level.

Recruitment: Patients will be recruited from the Women's Center for Bladder and Pelvic Health, the Midlife Health Center, and Western PA Women's Healthcare Associates. Women will be approached for study participation if they have symptomatic mild (stage I-III) POP, as measured by POP-Q exam, ¹¹ and have chosen to proceed with PFPT for management. Inclusion/exclusion criteria are listed below.

Inclusion criteria:

- Women in good health aged 40-80
- Has symptoms of pelvic organ prolapse; answers "yes" to at least 1 of the following questions:
 - Do you feel or see a vaginal bulge?
 - Do you feel pressure in the vagina?
- Meets POP-Q criteria on exam for stage I, II, or III prolapse
- Interested in PFPT for management of POP
- Normal mammogram within 1 year of enrollment

Exclusion criteria:

- Prior surgery for prolapse
- Other prior interventions for prolapse (e.g. pessary, PFPT)
- Connective tissue diseases known to affect collagen or elastin remodeling
- Known liver dysfunction
- Unevaluated abnormal vaginal bleeding or abnormal pap smear in the previous year
- BMI > 35 kg/m^2
- History of estrogen therapy (including birth control) in the previous year
- Current or prior breast or pelvic malignancy (ovarian, tubal, uterine, cervical or vaginal)
- Contraindication to hormone use (e.g. thromboembolic disorder, use of anti-coagulants, coronary artery disease, history of stroke)

Interventions - Baseline Visit:

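### Between-arm tests of the twice-measured secondary outcomes use unadjusted change scores, which are valid but usually less precise than adjusting for the baseline value already collected

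*Combined protocol and SAP*

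**What the plan says.** The Data analysis section gives one between-arm method for outcomes measured twice: a Student's t or Mann-Whitney U test, used to "compare the change between the baseline and 6-month measurements between groups". The paired tests in the same paragraph compare visits, not arms. Regression appears once, for a different purpose: "multivariable linear regression models will be used to examine the associations between clinical and biochemical outcomes".

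The baseline values are already collected:

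- Questionnaires (Interventions – Follow-up, item II.a): "Subjects will complete the same 3 questionnaires that they completed at their baseline visit".
- POP-Q (Aim 2): "POP-Q exam will be performed at baseline and 6 months after treatment".
- Collagenase (Aim 3): "Vaginal tissue swabs will be collected at baseline and 6 months".

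The primary outcome is different. It appears only among the 6-month activities ("The Patient Global Impression of Improvement questionnaire (PGI-I) will also be completed"), so it has no baseline value and this point does not touch it.

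On sample size the plan states: "A convenience sample size of 53 patients (27 in the treatment group and 26 controls) was chosen to comply with the budget".

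**The concern.** Analysing change is the same as subtracting the whole baseline value from the 6-month value, that is, assuming a slope of exactly 1. When the true slope is lower, as it is with equal SDs and a correlation below 1, the subtraction over-corrects and adds baseline noise to the treatment estimate. ANCOVA estimates the slope from the data.

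What is at stake is precision, not bias. In a pilot's secondary outcomes that is a modest matter, but there are three reasons to act:

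- Aim 2 (POP-Q) and Aim 3 (collagenase) rest entirely on twice-measured outcomes.
- The sample size is set by the budget, so more women are not an option.
- The data are meant to support a larger trial, so the between-arm estimates and their intervals are a main product.

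**Working it through.** **Inputs from the protocol.** 27 and 26 women; two-sided 0.05; outcomes measured at baseline and 6 months. The protocol gives no SD and no baseline/6-month correlation, so both are assumed below and shown over a range.

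**The plan's own figure.** The Sample size section states 99.6% power for a 48% difference, based on primate data. It cannot be reproduced without an SD. Read as a difference in means, it implies a standardized effect of about 1.27 (normal) to 1.29 (t). Nothing below depends on it.

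**Formulas.** Let r be the correlation, k = SD(6 months)/SD(baseline), and work in baseline SD units.

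- Change score: variance per woman = 1 + k² − 2rk.
- ANCOVA: variance per woman = k²(1 − r²), times 1 + 1/(N − 4) = 1 + 1/49 = 1.020 for estimating the slope.
- Multiplier for a difference between arms: √(1/27 + 1/26) = 0.275.
- True slope = rk. Before the 1.020 penalty, the change-score variance exceeds the ANCOVA variance by exactly (1 − rk)², so the gain vanishes only when the slope is 1.

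**Example, k = 1 and r = 0.5.** Change: 1 + 1 − 1 = 1.00. ANCOVA: 0.75 × 1.020 = 0.765. The ratio is 0.765, equivalent to 53/0.765 = 69.3 women. The 95% CI half-widths are 2.008 × 1.00 × 0.275 = 0.552 and 2.009 × √0.765 × 0.275 = 0.483.

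**Equal SDs (k = 1).** Power is from the noncentral t distribution for an assumed 0.6 SD effect.

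| r | Variance ratio ANCOVA/change | 53 women are worth | Half-width, change → ANCOVA (SD) | Power, change → ANCOVA |
|---|---|---|---|---|
| 0.3 | 0.663 | 79.9 | 0.653 → 0.532 | 44% → 60% |
| 0.5 | 0.765 | 69.3 | 0.552 → 0.483 | 57% → 69% |
| 0.7 | 0.867 | 61.1 | 0.427 → 0.398 | 79% → 84% |
| 0.9 | 0.969 | 54.7 | 0.247 → 0.243 | 99.8% → 99.8% |

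**Unequal SDs.** Eligibility restricts baseline POP-Q ("Meets POP-Q criteria on exam for stage I, II, or III prolapse"), so equal SDs are not assured. Variance ratios with the penalty included:

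| k | r = 0.3 | r = 0.5 | r = 0.7 | r = 0.9 |
|---|---|---|---|---|
| 0.8 | 0.51 | 0.58 | 0.64 | 0.62 |
| 1.0 | 0.66 | 0.77 | 0.87 | 0.97 |
| 1.2 | 0.78 | 0.89 | 0.99 | 1.00 |
| 1.4 | 0.86 | 0.96 | 1.02 | 0.86 |

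At k = 1.4 and r = 0.7 the slope is 0.98, and ANCOVA is about 2% worse. At k = 1.2 and r = 0.7, power for 0.6 SD moves only from 69.1% to 69.6%.

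**Chance imbalance.** The SE of a baseline difference is 0.275 SD, so a difference above 0.25 SD arises in about 36% of randomizations (two-sided normal tail beyond 0.25/0.275). The change score leaves (1 − slope) times that difference in the estimate. With k = 1, a one-SE imbalance moves it by 0.19, 0.14, 0.08 or 0.03 SD at r = 0.3, 0.5, 0.7 or 0.9. This averages to zero over randomizations.

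**Simulation.** With 27 v 26, normal data and equal SDs (10,000 trials per setting), rejection under the null was 4.7–5.1% for the change t-test, 4.8–4.9% for Mann-Whitney and 4.7–5.3% for ANCOVA. For a 0.8 SD effect, power for change t / Mann-Whitney / ANCOVA was 68/65/84% at r = 0.3, 81/79/90% at 0.5 and 96/95/98% at 0.7. Simulated variance ratios agreed with the formula to about 0.01.

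**The case against.** The strongest reply is that this is an efficiency preference. The planned test is unbiased and holds its level, the outcomes are secondary, the trial is a pilot, and the primary outcome is untouched. All of that stands, and it limits how much weight the point can bear.

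Other parts of the reply also hold:

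- Chance imbalance and lost precision are one quantity, as the (1 − rk)² identity shows. The 36% figure is not a second harm. It describes the imbalance, not the error: at slope 0.7, a 0.25 SD imbalance moves the estimate by 0.3 × 0.25 = 0.075 SD, against a half-width of 0.43.
- Aim 2 and the outcome list name POP-Q stage, which is ordinal. No gain has been computed for stage, for rank-ANCOVA or for log collagenase, so the figures do not carry over to them.
- The size is unknown without r and the SDs. It can be near zero, and with an SD ratio below 1 it exceeds the equal-SD figures.
- If the effect implied by the stated 99.6% is taken as 1.27 baseline SDs, change-score power with equal SDs is already 97% or more at r = 0.3 and above.

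The last point does not settle the matter. That effect comes from primate collagen and collagenase data, cannot be checked, and says nothing about the questionnaires or POP-Q. None of these points makes the change score the better default, because adjustment costs about 2% in variance at worst and may save a third or more.

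**Conclusion.** The concern holds as a loss of precision, not an error of validity. With equal SDs and correlations of 0.3 to 0.9, baseline adjustment would reduce the variance of the between-arm difference by about 34% down to 3%. It would save more if the 6-month SD is smaller than the baseline SD, and little or nothing if the slope is near 1. The direction is secure under a linear model apart from the 2% penalty, but the magnitude rests on assumed inputs. The figures apply to roughly normal continuous outcomes, not to POP-Q stage or to a Mann-Whitney analysis.

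**What to change.** In the Data analysis section, make the between-arm analysis of PFDI-20, PISQ-12, PFIQ-7, continuous POP-Q measurements and collagenase a linear model of the 6-month value on randomized arm and baseline value. Report the adjusted difference with its 95% CI. For skewed data, such as collagenase may be, use a log transformation or rank-ANCOVA. These estimate different things, so settle the choice before allocation is revealed. For POP-Q stage, use a baseline-adjusted ordinal model or rank-ANCOVA; the stability of an ordinal model in 53 women has not been checked here. Keep the planned change-score test as a sensitivity analysis. PGI-I needs no change on this point.

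The cost is SAP wording and, for each linear model, one degree of freedom, a variance penalty of about 2% at N = 53. No new data are needed.

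### Safety withdrawal is from the whole study, and the PGI-I is collected only at 6 months, so a woman withdrawn earlier has no primary outcome and the arm comparison may be biased

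*Combined protocol and SAP*

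**What the plan says.** The Safety Monitoring section sets out graded responses. Women report symptoms: "Patients will be instructed to contact the research team in the event of any symptoms, such as breast tenderness, perineal pain, vaginal discharge, or bleeding". A lesser step follows: "Persistent breast or perineal pain may require a decrease in the frequency of vaginal estrogen use". Bleeding is worked up under usual clinical guidelines. The last step is at the investigators' discretion: "if continued study participation is felt to be unsafe for any woman, she will be withdrawn from the study". Stopping the cream while remaining in follow-up is not described.

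The end of the Follow-up section names the endpoint: "Primary outcome: Global impression of improvement with treatment, as measured by the PGI-I". The PGI-I is not among the baseline questionnaires, which are the PFDI-20, PISQ-12 and PFIQ-7. The 3-month contact is a telephone call "to assess compliance with therapy and to address questions". The PGI-I appears only at the visit held "6 months after initiation of therapy", where item II.a adds it to the other three: "The Patient Global Impression of Improvement questionnaire (PGI-I) will also be completed".

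The Sample size paragraph gives 27 women on estrogen and 26 controls, with no allowance for dropout. The Data analysis section names tests but no analysis population and no treatment of missing values.

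**The concern.** The primary outcome has one measurement, at the end. A woman who leaves the study before month 6 has neither a baseline nor an interim PGI-I to stand in for it. One written rule, followed literally, takes women out of the study for a reason that may be related both to the treatment and to how they would have rated it. If more women leave one arm, and those women would have rated themselves differently from the women who stayed, comparing those who remain no longer compares the groups as randomized.

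The plan itself ties these risks to estrogen. The symptom list comes straight after its statement on the risks of vaginal estrogen, and the handouts describe estrogen side effects. An excess of safety withdrawals on estrogen is therefore a reasonable worry. Each woman lost is about 4% of an arm (1/27 = 3.7%, 1/26 = 3.8%). The pilot is also meant to be the basis for a larger trial, so a distorted estimate would be carried forward.

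**Working it through.** **The plan's own figure.** The only design calculation is 99.6% power for a 48% difference with 53 women at two-sided 0.05. It rests on primate collagen and collagenase data, not on the PGI-I, and gives neither an SD nor group rates, so it cannot be reproduced from its stated inputs. Read as two proportions 48 points apart, power runs from 96.0% (26% v 74%) to 99.5% (0% v 48%). Read as a mean difference of 0.48, it needs an SD of about 0.37 to 0.38. It does not bear on this point.

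**Inputs from the documents.** Arms of 27 and 26; one PGI-I per woman, at 6 months; two-sided 0.05.

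**Assumptions, none of them in the documents.** There is no true difference. The outcome is roughly normal, scaled so that higher is better. A withdrawn woman has no PGI-I and is left out of the analysis. On estrogen k women are withdrawn, and on placebo j. The women withdrawn are drawn at random from the worst-rated half, or the worst-rated 40%, of their arm.

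**Mean shortfall m of a withdrawn woman.** For the lowest fraction p of a standard normal, m = φ(z_p)/p.
- p = 0.5: 0.3989/0.5 = 0.798 SD
- p = 0.4: 0.3863/0.4 = 0.966 SD

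**Shift in the observed difference** (positive favours estrogen) = m·k/(27 − k) − m·j/(26 − j).

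| Withdrawn, estrogen v placebo | m = 0.798 | m = 0.966 |
|---|---|---|
| 1 v 0 | 0.031 | 0.037 |
| 2 v 0 | 0.064 | 0.077 |
| 3 v 0 | 0.100 | 0.121 |
| 5 v 0 | 0.181 | 0.220 |
| 4 v 1 | 0.107 | 0.129 |
| 2 v 2 | −0.003 | −0.003 |
| 0 v 3 | −0.104 | −0.126 |

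Example: 5 v 0 with m = 0.966 gives 5 × 0.966/22 = 0.220.

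**Outer range.** Let g be the amount, in SD, by which withdrawn estrogen women would have rated themselves worse than those who stayed. With no placebo withdrawals the shift is g·k/27. At k = 5 and g = 1.5 it is 0.278. At k = 5 and g = −1, where the women withdrawn were doing better, it is −0.185.

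**Scale.** The standard error of the difference is √(1/27 + 1/26) = 0.275 SD with everyone measured. It is 0.277 to 0.290 SD after 1 to 5 estrogen losses.

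**Error rate.** In simulation of the same estrogen-only scenarios with a t-test, shifts are close to the table or slightly smaller. Two-sided type I error is about 5% to 6% for 1 to 2 losses and about 6% to 11% for 3 to 5.

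**Precision.** This is a minor cost. The effect detectable with 80% power goes from 0.785 SD (27 v 26) to 0.809 SD (24 v 26).

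**The case against.** The strongest reply is that the listed symptoms prompt a call to the team, not withdrawal. Less frequent dosing and a bleeding work-up come first, and only a judgement that continuing is unsafe ends participation. The rule covers any woman in either arm of a placebo-controlled trial with blinded research staff. The plan calls the risks small and gives no withdrawal rate. The text does not forbid asking a withdrawn woman for her questionnaire, and it does not specify a complete-case analysis. The bias needs both. Finally, being unsafe to continue need not track improvement in prolapse, which is what the PGI-I rates.

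Most of this stands. A reader might infer that the PGI-I is lost in women with adverse events generally. The documents do not support that, because most events would be handled short of withdrawal. A reader might also infer that the comparison is biased toward estrogen. That needs both more withdrawals on estrogen and poorer ratings among the women withdrawn, and the documents give figures for neither.

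It does not follow that this is only a missing detail. The one consequence written for an unsafe participant is to leave the study, and the one primary measurement comes at the end of it. Staff following the text would have no reason to collect that measurement.

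**Conclusion.** The point holds as a risk of bias of unknown direction. As written, a safety withdrawal before month 6 leaves no primary-outcome value, and nothing in the plan says how that gap is handled. If women with poorer ratings are lost from estrogen only, 1 or 2 losses move the difference by about 0.03 to 0.08 SD, small against a standard error of about 0.28 SD. Three to five losses (11% to 19% of that arm) move it by about 0.10 to 0.22 SD, up to roughly 0.8 of a standard error. That is an unfavourable case, not an expectation. With equal losses the shift is about 0, and it reverses if the losses fall on placebo or on women doing well. All these counts and ratings are assumed. The case for acting is that the change is cheap and removes this source of bias, whatever its sign, for every woman whose questionnaire is obtained.

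**What to change.** Leave the investigators' safety decision unchanged. Add to the Follow-up section that, unless a woman withdraws consent, her 6-month PGI-I, PFDI-20, PISQ-12 and PFIQ-7 are still sought after any safety stop, by mail or telephone if she cannot attend. Add to the Data analysis section that every woman is analysed in her randomized arm, that withdrawals and their reasons are reported by arm, and that a short sensitivity analysis covers any PGI-I still missing.

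The cost is a few sentences and a few extra contacts; the 6-month visit and its $50 payment are already planned. The downside is that some women will be rated after a shorter exposure, so the estimate describes the effect of assignment to estrogen rather than of completing it.
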